7.3.4 Final Study Visit

The final study visit will occur at the routine 4 week post-TIPS follow up IR clinic visit. Final assessments of MHE and QOL will occur and the final home stool collection kits will be provided.

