Precis: A total of 40 patients taking proton pump inhibitors (PPIs) who undergo transjugular intrahepatic portosystemic shunt (TIPS) creation as part of routine clinical care will be randomized in 1:1 fashion to either continue or discontinue their PPIs to determine whether these commonly used gastric acid suppressing agents increase risk of post-TIPS hepatic encephalopathy (HE). Patients will be assessed for symptoms of minimal HE (MHE), using the established psychometric hepatic encephalopathy score (PHES) battery of tests. MHE assessment will be conducted at two timepoints: at baseline prior to randomization and TIPS creation and approximately 4 weeks after randomization and TIPS creation. Stool samples will also be collected at both timepoints to allow characterization of the gastrointestinal (GI) tract microbiome using 16S rRNA sequencing. The pre to post-TIPS change in PHES scores will be compared between patients randomized to continue versus discontinue their PPIs. Quality of life (QOL) will also be assessed. Changes in the GI tract microbiome will be analyzed to determine whether this represents a potential biological mechanism linking PPI use with post-TIPS HE.

Objectives: The primary objective is to determine whether discontinuation of PPIs reduces the risk of post-TIPS HE. Additional secondary objectives will include a comparison of cirrhosis-specific and gastroesophageal reflux disease-specific QOL in the PPI continuation and discontinuation groups. An exploratory objective is to determine whether PPI induced changes in the GI tract microbiome represent a potential biological mechanism mediating PPI-induced risk of post-TIPS HE.

Endpoints: Change in PHES pre to post-TIPS by intention-to-treat (ITT) (primary endpoint). Per-protocol change in PHES; change in Chronic Liver Disease Questionnaire (CLDQ) and Quality of Life in Reflux and Dyspepsia (QOLRAD) scores pre to post-TIPS (secondary endpoints). Mediation analysis of GI tract bacterial taxon abundances as a potential link between PPI use and post-TIPS HE (exploratory endpoint).

Population: 40 male and female Duke University Hospital patients over the age of 18 taking PPIs and undergoing TIPS placement as part of routine clinical care

Phase: 2

[figure not shown]
Number of Sites Enrolling Participants: 1

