Description of Study Intervention: Patients will be randomized to receive instructions to stop their existing PPI therapy (experimental/discontinuation/deprescribing arm) or to receive no specific instructions regarding PPI therapy (control/continuation arm)

Study Duration: Approximately 24 months

Participant Duration: Approximately 6-8 weeks

Schematic of Study Design

1 Key Roles

Principal Investigator:

[name]. Ph.D.

Duke University Medical Center

[name]

[name]

Email: [contact]

[contact]

Lead Clinical Research Coordinator:

[name], C.R.C.

Duke University Medical Center

[name]

[name]

Email: [contact]

[contact]

2 Introduction: Background Information and Scientific Rationale

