2.1 Background Information

Transjugular intrahepatic portosystemic shunt (TIPS) creation is an important minimally invasive procedure for treatment of complications resulting from cirrhosis and portal hypertension (1). Despite the beneficial effects of TIPS on ascites, gastrointestinal (GI) variceal bleeding risk, and in certain settings survival (2, 3), development of hepatic encephalopathy (HE) after TIPS can limit use of this procedure. HE is the most common complication of TIPS, occurring in 30% to 60% of patients (4). Medical therapy for HE, though effective, can be expensive (5) and cause unpleasant side effects (6). Thus, in patients who experience post-TIPS HE, the reduction in quality of life (QOL) can negate other beneficial effects of TIPS (7, 8). Furthermore, the cost of HE related care is substantial, estimated at \$5,370-\$50,120 per patient per year (9). Therefore, additional strategies to reduce the risk of post-TIPS HE are needed.

Recent retrospective studies have shown an association between proton pump inhibitor (PPI) use and HE in cirrhotic patients (10-20). Meta-analyses have supported a small but significantly increased risk of HE among cirrhotic patients taking PPIs, with pooled odds ratios ranging from 1.50 to 2.58 (21-24). Among these studies, two focused exclusively on TIPS patients and described a more robust effect size in this high risk population with a greater than 3 fold increased risk of post-TIPS HE among PPI users (19, 20). In an independent, unpublished dataset of 86 TIPS patients, we have further replicated the dose dependent association between PPI use and post-TIPS HE (Figure 1).

[figure not shown]

Figure 1: Patient timelines after TIPS showing intervals of PPI use and episodes of HE (left panel). Incidence rate ratios showing statistically significantly increased rates of post-TIPS HE with PPI use (middle panel) and with increasing PPI dosages (right panel).

Biological mechanisms to account for the association between PPI use and HE remain unknown, but a potential pathway involves alterations in the GI tract microbiome. Randomized placebo controlled studies have demonstrated that PPI use leads to distinct changes in the microbiome (25). These changes, characterized by colonization of the lower GI tract by oral flora not destroyed in a more alkaline stomach, appear to be reversible upon discontinuation of PPIs (25, 26). Separate observational studies have characterized the differences in GI flora

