4.1 Description of the Study Design

The proposed study is a single center randomized, open-label, deprescribing trial of PPI users undergoing TIPS creation. The study will involve two arms: the experimental/PPI discontinuation arm will be instructed to stop taking their PPIs prior to TIPS creation and the control/PPI continuation arm will receive no special instructions regarding their preexisting PPI medication. Patients will be assessed for MHE using the PHES test battery and for QOL using the CLDQ and QOLRAD surveys prior to randomization, and approximately 6-8 weeks later after TIPS creation. Stool samples will be collected at both time points. After the second and final assessment approximately 4 weeks after TIPS creation patients will have completed the study.

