7.1 Study Procedures/Evaluations

7.1.1 Study Specific Procedures

The following will study specific procedures will occur:

- Prior to randomization, all patients will undergo assessment of MHE, using the established PHES battery of pencil-and-paper tests (Figure 3), QOL assessments using the CLDQ and QOLRAD surveys, and will be provided with return-by-mail at home stool collection kits
- Patients will be randomized to either receive instructions to immediately discontinue their PPI, or to receive no specific instructions regarding their PPI
- Patients in the PPI discontinuation arm will receive intermittent phone call reminders encouraging them to refrain from PPI use, to attempt lifestyle interventions to counteract GERD symptoms (e.g. smoking cessation, avoiding late evening meals, and head-of-the-bed elevation) (40), and to use on-demand over-the-counter histamine H2 blocker therapy for intolerable GERD symptoms
- Approximately 4 weeks following TIPS creation, all patients will undergo reassessment of MHE and QOL and will be provided with return-by-mail at home stool collection kits
- At the completion of the study, all patients will be invited to resume or discontinue PPI therapy at their discretion and upon discussion with their primary care, gastroenterology, and IR physicians

Psychometric Hepatic Encephalopathy Score

Test	Description
Number connection test A (NCT-A)	Randomly dispersed numbers are to be connected with each other in serial order as quickly as possible.
Number connection test A (NCT-B)	Randomly dispersed numbers and letters are to be connected in alternating series (1-A-2-B...) as quickly as possible.
Digit-symbol	Digits from 1 to 9 are assigned respective symbols. Under each digit the corresponding symbol is to be written within a given time.
Serial dotting	Draw a dot inside each circle as quickly as possible.
Line tracing	A given line is to be traced as quickly as possible.

Figure 3: PHES tests from (41).

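### Only the hand-out of home stool kits is scheduled, so the final sample follows the final PHES and may follow study completion, the baseline sample may follow the Day 1 stop-PPI call, and no stated field dates either sample

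*Combined protocol and SAP*

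**What the plan says.** **Intent.** The synopsis places the two assessments "at baseline prior to randomization and TIPS creation and approximately 4 weeks after randomization and TIPS creation" and adds: "Stool samples will also be collected at both timepoints". Section 4.1 repeats that stool is collected at both.

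**Procedures.** Sections 7.1.1, 7.3.2 and 7.3.4 and the schedule in 7.3.7 tie only the kit to the visit. Kits are given out at the pre-TIPS clinic visit (Day 0) and again at the post-TIPS visit (about Day 42). Of that later point, 7.1.1 says "all patients will undergo reassessment of MHE and QOL and will be provided with return-by-mail at home stool collection kits", and 7.3.4 says "Final assessments of MHE and QOL will occur and the final home stool collection kits will be provided". Under 7.2.3 the sample is taken at home and posted back. The only time figure given for it is a room-temperature storage limit of 60 days.

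**PPI instructions.** Randomization is on Day 1 (7.3.7). The discontinuation arm is then telephoned and told to stop (7.3.3), with immediate effect (7.1.1).

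**Completion.** Section 4.1 says: "After the second and final assessment approximately 4 weeks after TIPS creation patients will have completed the study". Section 7.1.1 says: "At the completion of the study, all patients will be invited to resume or discontinue PPI therapy at their discretion". Section 7.9 agrees.

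**Records.** The CRF contents listed in section 11 include PHES, QOL and on-demand acid-suppressant use, but no stool collection date. The labels in 7.2.3 are described only as serving traceability.

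**The concern.** In the mediation model of section 10.4.3, the mediator is each patient's pre-to-post change in taxon abundance, regressed on randomized arm (path a). That change is meaningful only if the first sample reflects the period before PPIs were stopped and the second reflects the assigned period. Section 2.1 says that PPI-related microbiome changes "appear to be reversible upon discontinuation of PPIs". A discontinuation-arm baseline sample taken after the call may therefore already contain part of the shift that path a is meant to capture. A final sample taken after a patient in either arm has changed PPI use may have lost part of the contrast.

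Section 10.4.11 already warns of low power, mediator measurement error, multiplicity and reverse causation. It does not mention sample timing. An analysis this limited has little room for avoidable dilution, and without a collection date the mistimed samples would be hard to pick out afterwards.

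**Working it through.** The plan states no figure on this point, so there is none to reproduce. The check is day arithmetic on the schedule, then the direction of any bias.

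**1. Baseline window.** Kit on Day 0; randomization and stop-PPI call on Day 1 (7.3.7). Window = 1 − 0 = about 1 day. Section 13.3.2 requires consent before any study procedure and consent is taken on Day 0, so the window cannot open earlier as the visits are laid out. Section 7.3.3 places randomization after the baseline assessments. However, 7.3.2 has PHES and QOL done at the visit and the kit merely supplied, and no text holds the call until a stool sample has been taken.

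**2. Final sample.** Final PHES and final kit are both at about Day 42: 42 − 42 = 0 days. A home sample from that kit comes after the PHES. If the second assessment in 4.1 means PHES and QOL, the sample also comes after completion, when PPI choice is released.

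**3. Is there a later end of study that covers stool return?** The synopsis gives "Participant Duration: Approximately 6-8 weeks". Section 4.1 uses the same 6–8 weeks for the interval between the two assessments: 6 × 7 = 42 days to 8 × 7 = 56 days. The participation period is therefore most simply the time between assessments and gives no sign of a period reserved for returning stool.

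**4. Can other dates stand in for the collection date?** Hand-out bounds collection from below and a logged receipt date, if there is one, from above. The bound is tight if return is prompt. It is loose if return is slow, because the 60-day storage limit exceeds the whole 42–56 days between assessments.

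**5. Direction of bias.** Let δ be the true shift in a taxon caused by stopping PPIs, and m the mean change without stopping. Section 10.4.3 codes X = 1 for continuation, so

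- true a = m − (m + δ) = −δ.

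Let L be the average fraction of δ lost in the discontinuation arm (late baseline sample, or PPI resumed before the final sample). Let G be the average fraction gained in the continuation arm (PPI stopped before the final sample). Then

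- observed a = (m + Gδ) − (m + (1 − L)δ) = −δ(1 − L − G).

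Any L or G above zero with L + G no greater than 1 shrinks path a towards zero. The documents give no return delay, no frequency of PPI change after completion and no time course for the taxa. L and G therefore cannot be estimated, and no power loss is computed.

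**The case against.** **The intended order is clear.** The synopsis puts baseline stool before randomization, and 7.3.3 randomizes after the baseline assessments. This stands as to intent: a reader might infer that the plan means to allow baseline sampling after the stop call, and the documents do not support that. The operational sections nevertheless do not secure the intended order.

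**Completion may include stool return.** Section 4.1 does not say whether the final assessment includes the stool sample. This stands, and it is why the sample only may follow completion. That it follows the final PHES needs no such reading.

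**Dates may be captured elsewhere.** Sections 7.5 and 8.3 add CRF items missing from the section 11 list, so that list may be incomplete, and a label could carry a date. Hand-out and receipt dates can also bound collection. A reader might infer that no timing sensitivity analysis would be possible; that goes too far. The supported statement is that no collection date is specified and that the substitutes may be loose.

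**The order of final PHES and stool matters little in itself.** Both the mediator and the outcome are changes over about six weeks, and same-day sampling would not place one before the other. This largely stands. Section 10.4.11 already concedes reverse causation, with rifaximin for overt HE as its example, and earlier sampling would not remove it. What can be avoided is a change in PPI use between the visit and the sample.

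**Only an exploratory endpoint is involved.** True, and it sets the severity.

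**Conclusion.** The point holds, as a minor one. Following the procedures as written puts the final sample after the final PHES and possibly after PPI choice is released in both arms. It also leaves about one day for a baseline sample before the stop-PPI call, against the synopsis's placement of that sample before randomization. This is more than missing detail, because the hand-out schedule itself produces the mistiming.

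The effect is confined to path a of the exploratory mediation analysis, and its size is unknown. The direction, towards zero, rests on section 2.1's statement on reversibility and on some patients sampling late or changing PPI use before they sample. A reader might infer a threat to the trial's main results; the documents do not support that, since PHES and QOL are measured at the visits and overt HE and adverse events do not depend on the stool sample.

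**What to change.** In 7.1.1, 7.3.2, 7.3.4 and 7.3.7:

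- (a) Send the final kit to both arms ahead of the visit at about Day 42, for collection before or on the day of that visit and before any change in PPI use at study completion.
- (b) At Day 0, after consent, ask all patients to collect the baseline sample before the Day 1 randomization call.
- (c) Record the date and time of collection and acid-suppressant use at each sample, for example on the label and a CRF field. Route this away from the CRC who does the PHES, who is blinded under 10.6.1.
- (d) Report the mediation analysis with all samples and, as a sensitivity analysis, with in-window samples only. Use the same cutoffs in both arms: baseline collected before randomization, judged by date and time so that a Day 1 sample taken after the call does not count; final collected no later than the date of the final visit.

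The investigators should also reconcile the synopsis and sections 4.1, 7.1.1, 7.3.3, 7.3.4 and 7.9 on when samples are taken relative to the PPI instructions. No PPI rule is proposed here.

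**Cost.** Text edits to four sections, earlier dispatch of one kit, and a small number of fields (on-demand acid-suppressant use is already collected; the additions are date, time and use at sampling). The kits and laboratory work stay the same. The baseline window is short and (b) is only a request, so some samples will miss it. The in-window analysis will then have fewer than the planned 40 patients, when 10.4.11 already says that about 50 are typically needed to detect large mediation effects. It should be read as a check on the all-sample result.

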7.3.5 Early Termination Visit

Not applicable.

7.3.6 Unscheduled Visit

Unscheduled visits related to complications from the TIPS procedure may occur as needed, per routine standard of care.

7.3.7 Schedule of Events Table

Procedures	Referral for TIPS (~Day -14)	Pre-TIPS IR clinic visit (Day 0)	Post-clinic phone call (Day 1)	PPI reminder phone call (~Day 7)	TIPS performed (~Day 14)	In person PPI reminder (Day 15)	PPI reminder phone call (~Day 28)	Post-TIPS IR clinic visit (~Day 42)
Screening by IR clinical team	X							
Informed written consent		X						
MHE assessment		X						X
QOL assessment		X						X
Stool sample		X						X

collection kit provided								
Randomization			X					
Reminder to refrain from PPI use				X		X	X	
TIPS procedure					X			

7.4 Justification for Sensitive Procedures

Not applicable.

7.5 Concomitant Medications, Treatments, and Procedures

All concomitant standard of care medications for post-TIPS HE (e.g. lactulose, rifaximin) deemed necessary by gastroenterology and IR physicians will be permitted. Use of such medications will be documented on case report forms (CRFs).

For GERD symptoms related to discontinuation of PPIs, patients will be encouraged to undertake lifestyle interventions (e.g. smoking cessation, avoiding late evening meals, and head-of-the-bed elevation) (40). If lifestyle interventions are inadequate to control GERD symptoms, patients may use on-demand over-the-counter histamine H2 blocker therapy. On-demand use of PPIs will be discouraged but permitted for refractory, intolerable GERD symptoms. Use of on-demand pharmacological agents will be recorded on the CRFs.

7.5.1 Precautionary Medications, Treatments, and Procedures

Not applicable.

7.6 Prohibited Medications, Treatments, and Procedures

Not applicable.

7.7 Prophylactic Medications, Treatments, and Procedures

Not applicable.

7.8 Rescue Medications, Treatments, and Procedures

Not applicable.

7.9 Participant Access to Study Intervention at Study Closure

After completion of the study patients will be informed that they may resume or discontinue their PPI based on their own preferences and in consultation with their primary care, gastroenterology, and IR physicians.

8 Assessment of Safety

8.1 Specification of Safety Parameters

Safety parameters included as secondary endpoints include episodes of overt HE and drug related AEs (see Section 4.2).

8.1.1 Definition of Adverse Events (AE)

Adverse event means any untoward medical occurrence associated with the use of an intervention in humans, whether or not considered intervention-related (21 CFR 312.32 (a)).

8.1.2 Definition of Serious Adverse Events (SAE)

An AE or suspected adverse reaction is considered “serious” if, in the view of the investigator, it results in any of the following outcomes: death, a life-threatening adverse event, prolongation of hospitalization, or a persistent or significant incapacity or substantial disruption of the ability to conduct normal life functions. Important medical events that may not result in death, be life-threatening, or result in prolongation of hospitalization may be considered serious when, based upon appropriate medical judgement, they may jeopardize the patient or subject and may require medical or surgical intervention to prevent one of the outcomes listed in this definition. Examples of such medical events include development of grade IV esophagitis, gastric or duodenal ulcers, or West-Haven grade 4 HE (e.g. comatose, unresponsive to pain, decorticate or decerebrate posturing).

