4.2.2 Secondary Endpoints

Secondary endpoints of the study will include a per-protocol analysis of the change in PHES pre versus post-TIPS in the PPI continuation versus discontinuation arm; an ITT analysis of the change in CLDQ and QOLRAD scores pre versus post-TIPS in the PPI continuation versus discontinuation arms; episodes of overt HE, defined as a West-Haven score greater than or equal to 2 (e.g. gross disorientation, drowsiness, asterixis, and inappropriate behavior), on-demand use of histamine H2 blockers or PPIs due to GERD symptoms, and AEs.

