7.1.2 Standard of Care Study Procedures

The following occur as standard of care for all patients undergoing TIPS creation:

- After receiving a referral TIPS creation, the treating IR physician reviews the patient's electronic medical records including history, medications, allergies, physical examination and imaging findings, and laboratory tests to evaluate the patient's candidacy for the procedure
- All patients referred for TIPS creation undergo a pre procedure consultation with the treating IR physician
- All TIPS procedures are performed under general anesthesia. Portal vein access is achieved using intracardiac echocardiography/intravascular ultrasound guidance. Controlled expansion covered Viatorr covered stent grafts are deployed and dilated to achieve a target reduction in the portosystemic pressure gradient of 50% or <12 mm Hg for varices and <8 mm Hg for ascites (1). Patients are admitted to the hospital following TIPS creation for post procedure observation.
- Patients undergo routine follow up with the IR clinical team approximately 4 weeks after TIPS creation.

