8.5 Study Halting Rules

The study intervention will be halted when three SAEs determined to be "definitely related" or "probably related" to PPI discontinuation are identified.

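### Section 8.1.2 makes prolonged hospitalisation a seriousness criterion but not a new inpatient admission, so an unplanned admission from home need not be classed as an SAE

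*Combined protocol and SAP*

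**What the plan says.** Section 8.1.2 defines an SAE by outcome, in the view of the investigator. The listed outcomes are "death, a life-threatening adverse event, prolongation of hospitalization", and "a persistent or significant incapacity or substantial disruption of the ability to conduct normal life functions". A second sentence adds a judgement route: "Important medical events that may not result in death, be life-threatening, or result in prolongation of hospitalization may be considered serious". It is followed by illustrations: "Examples of such medical events include development of grade IV esophagitis, gastric or duodenal ulcers, or West-Haven grade 4 HE".

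The hospital stay that the protocol plans is described in Section 7.1.2: "Patients are admitted to the hospital following TIPS creation for post procedure observation". In the schedule of events (Section 7.3.7), TIPS falls at about Day 14 and an in-person reminder at Day 15. The remaining study contacts are clinic visits or telephone calls.

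SAE status is used in three other places:

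- **Halting (Section 8.5):** "The study intervention will be halted when three SAEs determined to be" definitely or probably related to PPI discontinuation. Section 10.4.7.1 restates the rule with the word related alone.
- **IRB reporting (Sections 8.4.1 and 8.4.2):** five business days for a reportable SAE; ten business days for an AE that needs prompt reporting but is not an SAE.
- **Recording (Section 8.3):** events are recorded up to 7 days after last participation if non-serious, and up to 30 days if serious.

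**The concern.** Prolongation presupposes a stay already under way. Participants in the discontinuation arm are told to stop their PPI at about Day 1, roughly two weeks before the TIPS admission, and after discharge they are followed to a clinic visit at about Day 42. That participants are outpatients for most of the study is an inference from this schedule, but a direct one. An admission from home during these periods meets no hospital criterion in Section 8.1.2.

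At stake is consistency in the study's one pre-set safety stop, in IRB reporting, and in late event capture. Two similar admissions could be classified differently without either classification breaching the protocol. Treatment is open-label for the treating physician (Section 10.6.1), and safety oversight rests with the PI (Section 8.6).

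**Working it through.** No figure in the plan can be reproduced here, because the threshold of three SAEs has no stated derivation. The check is therefore mainly textual.

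**1. Is admission covered elsewhere?** The outcome list gives four items, and admission is not one of them. The important-medical-event sentence repeats prolongation alone, so the wording is consistent and does not look like a slip in one place. No other section supplies an admission criterion.

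**2. Do the other criteria capture admissions anyway?** They can, but they need not. The disruption criterion depends on the investigator's view. The important-medical-event route is permissive: such events "may be considered serious when, based upon appropriate medical judgement". Its only HE example is West-Haven grade 4, whereas the secondary endpoint covers "episodes of overt HE, defined as a West-Haven score greater than or equal to 2". An admission for grade 2 or 3 HE is named nowhere in Section 8.1.2. Grade IV esophagitis and ulcers are named; an admission for bleeding without one of those diagnoses is not.

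**3. What follows from a non-serious classification?**

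| Safeguard | Classed as SAE | Classed as non-serious |
|---|---|---|
| Halting count (8.5) | Counts if definitely or probably related to PPI discontinuation | Does not count |
| IRB report (8.4.1, 8.4.2) | Five business days, if reportable | Ten business days if prompt reporting is required or it is an unanticipated problem (8.4.3); otherwise no stated deadline |
| Recording after last participation (8.3) | 30 days | 7 days |

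Taking the final visit at about Day 42 as the last day of participation, the recording limits are 42 + 7 = Day 49 and 42 + 30 = Day 72. An admission starting between about Day 50 and Day 72 falls within the recording window only if it is an SAE. The separate window in Section 7.3.3, 30 days from TIPS, ends at about 14 + 30 = Day 44 and does not close this gap.

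**4. Illustration of the halting count.** All rates are assumptions; the documents give none. Let p be the risk per patient of an event that is definitely or probably related to PPI discontinuation and is an SAE once admissions count. Take 20 discontinuation-arm patients (Section 10.5) with at most one event each. The chance of reaching three is 1 − Σ(k = 0 to 2) C(20, k) p^k (1 − p)^(20 − k). If a share s of these events qualifies only through admission and is not counted, p becomes p(1 − s).

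| Assumed p | All counted | s = 0.25 | s = 0.50 |
|---|---|---|---|
| 0.10 | 0.323 | 0.186 | 0.075 |
| 0.20 | 0.794 | 0.595 | 0.323 |
| 0.30 | 0.965 | 0.861 | 0.595 |

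The table shows only that the count would be sensitive to the omission if related, admission-only events occurred. It does not show that they will.

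**The case against.** The strongest reply is that the practical consequence is small. Much of this stands.

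- **Halting needs attribution as well as seriousness.** Under Section 8.2.2, probably related requires that other factors be unlikely. Section 2.1 calls HE the most common complication of TIPS, and the trial's hypothesis is that stopping PPIs reduces HE. Many HE admissions would fail the relatedness test, so adding an admission criterion may seldom change the count for HE.
- **The other criteria apply on every study day.** Death, life-threatening events, incapacity or disruption, and important medical events are not tied to inpatient time. Gross disorientation could reasonably be judged a substantial disruption. Grade IV esophagitis and ulcers, which are acid-related harms, are named explicitly.
- **There are other safeguards.** Non-serious AEs go on the CRF regardless of relationship (Section 8.3), overt HE is a secondary endpoint in its own right, AE proportions are compared whatever their seriousness (Section 10.4.3), and Section 5.5 allows suspension for unacceptable risk without three SAEs.

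A reader might infer more than the documents support:

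- **That admission for bleeding or HE is the typical serious event after stopping PPIs.** The trial data in Section 2.3.1 on abrupt discontinuation report reflux symptoms and endoscopic esophagitis, with no ulcers or esophagitis complications in the discontinuation arm (patients with ulcers or grade IV esophagitis had been excluded).
- **That the 30% to 60% HE rate in Section 2.1, or 6 to 12 of 20 patients (0.30 × 20 and 0.60 × 20), sizes the gap.** That rate is overall post-TIPS HE with no follow-up window given. It counts neither admissions nor events related to discontinuation.
- **That every admission is reported at ten rather than five business days.** Each deadline covers only a subset of events, as the table above shows.

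None of these points supplies the missing criterion. Classification of a new admission is still left to judgement.

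**Conclusion.** The gap is real and narrow. Followed exactly, Section 8.1.2 allows an unplanned inpatient admission to be filed as non-serious, with the three consequences set out above for halting, IRB reporting and recording. The point rests on the current text and on the visit schedule, not on any assumed rate.

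Its size is unknown: the documents give no admission rate, no share of admissions that would meet no other criterion, and no rate of events related to discontinuation. It does not mean that admissions go unrecorded, since those starting within the 7-day window still reach the CRF, nor that the halting rule cannot work. The correction is worth making because it is cheap and concerns the only pre-set safety stop.

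**What to change.** In Section 8.1.2, change the hospital criterion to *new (unplanned) inpatient hospitalization or prolongation of hospitalization*, and make the same change in the important-medical-event sentence. State that the planned TIPS admission is not itself an SAE.

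In the same amendment, reconcile Sections 8.5 and 10.4.7.1. The first requires a definite or probable relationship and halts the study intervention; the second says only related and halts the study. Which wording applies is for the study team to decide.

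The cost is a short amendment with IRB review and some additional SAE forms. The change affects how events are classified; it alters neither treatment nor the threshold of three.
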